C.1. Overall Study design. This is an investigator initiated study supported in part by Depomed, Inc. We propose a 2-arm, double blind, parallel randomized controlled trial of FPNS and placebo for cancer patients with breakthrough dyspnea (Figure 1). The main goal of this study is to determine the effect size for both FPNS and placebo arm to inform a larger, adequately powered confirmatory randomized controlled trial. After study consent, eligible patients will be asked to complete a number of surveys and a 6-minute walk test at baseline, rest until they return to baseline dyspnea, and then do a second 6-minute walk test 20 minutes after they have been given either FPNS or placebo prophylactically. They will then rest again to return to baseline dyspnea, and then do another 6-minute walk test 20 minutes after repeating the same dose of either FPNS or placebo (with at least 30 minutes between the first and second dose). This design will allow testing of both single and repeated dosing on dyspnea under a double blind design.

Based on our experience conducting symptom control trials, this study will take between 1.5-2 hours to complete on a single visit. We believe this study design is feasible and would not add undue burden for patients. Patients will be compensated with a \$50 gift card for their time and effort.

C.2. Eligibility Criteria. The eligibility criteria are shown in Table 2.

Table 2. Study Eligibility Criteria

[figure not shown]

Figure 1. Study Flow Chart

Inclusion Criteria

1. Diagnosis of cancer
2. Breakthrough dyspnea, defined in this study as dyspnea on exertion with an average intensity level $\geq 3/10$ on the numeric rating scale
3. Outpatient at MD Anderson Cancer Center seen by the Supportive Care Service or Thoracic Medical Oncology
4. Ambulatory and able to walk with or without walking aid
5. On strong opioids with morphine equivalent daily dose of 80-500 mg, with stable (i.e. +/- 30%) regular dose over the last 24 hours
6. Karnofsky performance status $\geq 50\%$
7. Age 18 or older
8. Able to complete study assessments

Exclusion Criteria

1. Dyspnea at rest $\geq 7/10$ at the time of enrollment
2. Supplemental oxygen requirement > 6 L per minute
3. Delirium (i.e. Memorial delirium rating scale > 13)
4. History of unstable angina or myocardial infarction 1 month prior to study enrollment
5. Resting heart rate > 120 at the time of study enrollment

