6. Systolic pressure > 180 mmHg or diastolic pressure > 100 mmHg at the time of study enrollment
7. History of active opioid abuse within the past 12 months
8. History of allergy to fentanyl
9. Unwilling to provide informed consent
10. Patients who currently have no evidence of disease

C.3. Study screening. A 2 step consent process will be used. First, a verbal consent will be obtained by the study staff to proceed with screening of potential participants for eligibility and to characterize their dyspnea using the dyspnea survey and the cancer dyspnea scale. Outpatients may be contacted by phone within 1 week prior to their scheduled clinic visit to informed them of this study so they can make necessary arrangements if interested in participating. Eligible patients will then be formally enrolled onto the study after they have signed the informed consent indicating a willingness for the patient to participate in the trial. The number of patients screened, approached, eligible and enrolled will be documented. Reasons for refusal for eligible patients will also be captured. Based on our experience with similar trials, we expect that a majority of patients will complete this study.

C.4. Randomization. A computer generated sequence in permuted blocks will be used to assign patients to either FPNS or placebo and provided via a secured website, stratified by baseline level of dyspnea NRS at rest at the time of enrollment (i.e. 0-3, 4-6). Biostatistics will set up a Randomization website. Investigational Pharmacy personnel will perform the randomization assignment.

C.5. Blinding. Both patients and the research staff conducting the assessment will be blinded to the treatment assignment. FPNS will be dispensed by Dispensing Pharmacy at MD Anderson. Placebo will be identical in appearance to the FPNS.

C.6. Research staff. An orientation will be held with research staff involved in this study to introduce them with the study design, and standardize the provision of each intervention.

C.7. Study Interventions. The supply of study medication (both FPNS and placebo) will be provided by Depomed, Inc. FPNS is FDA approved (NDA 022569/S-007) for treatment of breakthrough cancer pain in opioid-tolerant patients. Immediately upon patient enrollment, the study physician will be notified and will determine the morphine equivalent daily dose (MEDD) in real time using standardized equianalgesic ratios.

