Placebo will be identical in appearance to the FPNS, and given to patients 20 minutes before the second and the third 6-minute walk test. Both the patient and the research staff conducting the assessments will be blinded to the nature of the intervention. During this entire study, patients will be monitored closely by trained research staff, and will have rapid access to medical care if needed.

Because this involves only 2 doses given to opioid tolerant patients, and under close monitoring by trained staff, we believe the dosing schedule proposed is safe.

C.8. Medication use during study. To minimize the co-intervention effect on dyspnea, patients will be advised to avoid using breakthrough opioids (for any reason) or bronchodilators for at least 2 hours prior to and during the study.

C.9. The 6-minute walk tests will be conducted based on guidelines from the American Thoracic Society (Laboratories 2002). Walking aid and supplemental oxygen via nasal prongs are allowed as long as patients keep them the same as before enrollment and during the entire study. This walking test allows patients to rest if they need to, and is highly acceptable to patients. It provides important information regarding patients' functional status, exercise capacity, and health-related quality of life (Guyatt *et al.* 1985, Guyatt *et al.* 1985). Before and after each test, we will be assessing the (1) dyspnea level with numeric rating scale and Borg scale, and the (2) respiratory rate and oxygen saturation. After each test, we will also be assessing (1) the distance walked at the end of each minute or portion of, (2) the total walking time, (3) the level of dyspnea at the end of each minute or portion of (NRS and Borg scale), and (4) the average walking speed.

The 6-minute walk test has excellent short term reproducibility (Guyatt *et al.* 1985), as well as good face, construct, and predictive validity (Du Bois *et al.* 2011), and changes in this test are concordant with changes in symptoms and mortality (Olsson *et al.* 2005). The minimal clinical significant difference is found to be 24-45 m for patients with idiopathic pulmonary fibrosis (Du Bois *et al.* 2011), and 86 m for patients with COPD.

The first 6-minute walk test was designed to provide important information regarding a patient's level of dyspnea on exertion, and to facilitate intra-individual comparison since there is significant variability in the expression of dyspnea among patients.

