Regulatory monitoring will be provided by the principal investigator, the Institutional Review Board (IRB), and the Data Safety and Monitoring Board (DSMB). Patient confidentiality will be ensured by use of study numbers, secure storage of clinical data, and anonymous reporting.

D. Statistical Analysis

D.1. Sample Size Calculation. Patients who have started the second walk test will be considered evaluable for this study's primary endpoint. 10 evaluable patients in the fentanyl arm provides 80% power to detect an effect size as small as 1.0 when alpha=5% using a two-sided paired t-test to compare dyspnea between the first and second walk tests. Results from this study will be used to calculate the sample size for an adequately powered randomized controlled trial.

D.2. Data Analysis. Summary descriptive statistics will be provided for demographics, outcomes, and other collected variables and will include proportions, medians, means, 95% confidence intervals, and other simple statistics as appropriate for the measure. Comparisons within arms will be performed using paired t-tests or signed rank tests.

E. Data Confidentiality Procedures

Health information will be protected and we will maintain the confidentiality of the data obtained from the patient's chart.

Collection of identifiers: We will collect and securely store patients' identifiers (including name, medical record number and demographic specifications). Each patient will be assigned a study number that will be the only identifier to figure in the analytical file and personal data will not be disclosed in any form. The key linking these numbers will be retained in a securely locked file by the investigator.

Data Storage: Protection of electronic and paper records will be guaranteed. All electronic records will be stored on password-protected institution computers behind the institution firewall. Any paper records will be classified and stored in locked files inside a locked office.

Training of personnel: Only MDACC personnel trained in maintaining confidentiality, the principle investigators and co-investigators, will have access to study records.

Data sharing: Study data will not be shared with any individuals or entities. The data will be kept by the principle investigator in a locked file cabinet.

Final disposition of study records: These data will be used only for this research study data files will be destroyed 5 years after publication of the findings.

F. References

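### C.4 stratifies by resting dyspnea but D.2 never uses the stratum, so an FPNS-versus-placebo comparison from plain arm summaries loses precision to the extent that resting dyspnea predicts the outcome

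*Combined protocol and SAP*

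**What the plan says.** C.1 describes the design: "We propose a 2-arm, double blind, parallel randomized controlled trial of FPNS and placebo for cancer patients with breakthrough dyspnea". On allocation, C.4 states: "A computer generated sequence in permuted blocks will be used to assign patients to either FPNS or placebo", and makes it "stratified by baseline level of dyspnea NRS at rest at the time of enrollment (i.e. 0-3, 4-6"). Patients with resting dyspnea of 7 or more are excluded in Table 2, so the two strata cover everyone who can be enrolled.

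Secondary objective 3 in section A asks for a comparison of FPNS with placebo on dyspnea, walk distance, neurocognitive function and adverse effects, from walk 1 to walk 2 and from walk 1 to walk 3.

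The analysis text is short. D.2 promises "proportions, medians, means, 95% confidence intervals, and other simple statistics as appropriate for the measure" and then: "Comparisons within arms will be performed using paired t-tests or signed rank tests". It names no between-arm method, and section D does not mention the stratum. D.1 sizes the study within one arm, "using a two-sided paired t-test to compare dyspnea between the first and second walk tests", and says that the results will feed the sample size of a larger trial. It does not say which SD will be used or how that trial will be analysed.

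**The concern.** Stratified blocks hold the arms nearly balanced on resting dyspnea. If resting dyspnea predicts the outcome, the difference in arm means then varies less from one randomisation to another than the ordinary two-sample standard error assumes, because that standard error still contains the between-stratum variation. The interval is too wide and the test rejects too rarely. The design has paid for balance, and the analysis gives the benefit away.

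What is at stake is precision in the only randomised comparison in the study, with about 10 patients per arm. There is also a question of bookkeeping: an SD that contains between-stratum variation and one that does not lead to different sample sizes for the confirmatory trial, and the plan does not say which will be carried forward.

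**Working it through.** **The plan's own figure.** D.1 states: "10 evaluable patients in the fentanyl arm provides 80% power to detect an effect size as small as 1.0 when alpha=5"%. For a two-sided paired t-test with n = 10 there are 9 degrees of freedom and the noncentrality is 1.0 × √10 = 3.16. The exact power is 80.3% (74.8% with n = 9). The figure reproduces. It is a within-arm calculation, so how the arms were balanced does not enter it.

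**Inputs for the between-arm check.**
- From the documents: two strata and permuted blocks (C.4); 10 evaluable patients in the FPNS arm (D.1).
- Assumed, because not stated: 1:1 allocation with 10 in the placebo arm; blocks of 4; normally distributed change scores; R², the share of within-arm variance of the change explained by the stratum, from 0 to 0.30.

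**Interval width.** In units of the unadjusted SD, the 95% half-widths are:
- without the stratum: t(18) × √(2/10) = 2.1009 × 0.4472 = 0.940
- with the stratum: t(17) × √(0.2 × (1 − R²)), where t(17) = 2.1098

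| R² | Half-width with stratum | Change from 0.940 |
|---|---|---|
| 0 | 0.944 | +0.4% |
| 0.05 | 0.920 | −2% |
| 0.10 | 0.895 | −5% |
| 0.20 | 0.844 | −10% |
| 0.30 | 0.789 | −16% |

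The break-even point is R² = 1 − (2.1009/2.1098)², about 0.008. Below it the lost degree of freedom costs more than the stratum returns. Simulation at R² = 0 gives a cost of 0.6% (mean half-width 0.934 against 0.928), hence about +0.5% overall.

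**Error rate.** In 20,000 simulated trials per setting (20 patients, equal strata, blocks of 4), the true two-sided error rate of an unadjusted two-sample t-test at a nominal 5% was 4.7%, 4.3%, 4.1%, 2.9% and 2.4% at R² = 0, 0.05, 0.10, 0.20 and 0.30. With the stratum in the model it stayed between 4.7% and 5.3%. A 25:75 split of the strata gave much the same picture.

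**What the walk-1 value does.** The change is measured from walk 1, so the walk-1 value is the natural second covariate. Suppose first that resting dyspnea acts on walk 2 only through walk-1 dyspnea (assumed correlations: 0.3-0.7 between rest and walk 1, 0.5-0.7 between walks 1 and 2). The stratum then explains only 1-8% of the variance of the change. The stratum alone alters the width by +0.1% to −3.6%, and the walk-1 value alone narrows it by 5-12%. Adding the stratum after walk 1 widens it again by 0.8-1.7%. Across all the scenarios tried, including some where the stratum has an effect of its own, the model with both covariates narrowed the interval by about 2-17% against the unadjusted comparison.

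**SD for the next trial.** The ratio of unadjusted to residual SD is 1/√(1 − R²): 1.05, 1.12 and 1.20 at R² = 0.10, 0.20 and 0.30. For an illustrative difference of 0.5 unadjusted SD, 80% power and two-sided 5%, n per arm = 2 × 7.849 × (1 − R²)/0.25. That is 63 with no adjustment, and 57, 51 and 44 at those three values.

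**The case against.** Four objections carry weight.

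- D.2 specifies no between-arm test or interval, so an unadjusted two-sample comparison is a supposition about how objective 3 would be met. This is correct, and the absence of any method for objective 3 is the more basic gap. The point is therefore conditional. It remains a separate one, because a plain two-sample test put into that gap would still ignore the stratum.
- A reader might infer that the study's main result is compromised. The documents do not support that. The primary objective and D.1 concern change within an arm, and balancing between arms leaves a paired test untouched.
- A reader might infer that the intervals will certainly be too wide. That depends on R², which the documents do not give. C.9 explains that the first walk serves comparison within the patient, "since there is significant variability in the expression of dyspnea among patients". The change score is thus already the plan's answer to that variability and may absorb much of what resting dyspnea would explain.
- A reader might infer that the unadjusted SD is an overstated input for the confirmatory trial. That holds only if that trial adjusts for the same covariates. If it neither stratifies nor adjusts, the total SD is the right input and the residual SD would under-size it. Sampling error is also larger than this effect: an SD on 18 degrees of freedom has a 95% interval of 0.76 to 1.48 times the estimate, so the derived sample size ranges from 0.57 to 2.19 times. The stratum accounts for 1.00 to 1.43 times over R² of 0 to 0.30.

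What remains after these is a precision gain that costs almost nothing. The sampling error of the SD cannot be avoided at this size, whereas ignoring the stratum can.

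**Conclusion.** The point holds as a conditional loss of precision in the secondary FPNS-versus-placebo comparison. If that comparison is made from unstratified summaries, the loss is nil at R² = 0, about 5% of interval width at 0.10 and about 16% at 0.30, and the test errs on the conservative side. No bias and no excess of false positives follow. The size rests on the assumed R², 10 patients per arm, 1:1 allocation and blocks of 4. The choice of SD for the confirmatory trial is left open by the plan rather than made wrongly, and needs a statement. A change to the wording is worth making before the data are analysed.

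**What to change.** In D.2, estimate each FPNS-minus-placebo difference (walk 1 to 2 and walk 1 to 3), with its 95% confidence interval, from a linear model with arm, the C.4 stratum and the walk-1 value of the outcome. Table 4 schedules no adverse-effect rating until just before walk 2, so for those outcomes the model would hold arm and stratum only.

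Report the SD of the change twice: unadjusted, and as the residual SD of the model. State in D.1 that the confirmatory trial will be sized with the one that matches its planned analysis, and with the residual SD only if that trial adjusts for the same covariates.

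The cost is wording. The stratum is needed for randomisation and the walk-1 values are already scheduled, so conduct does not change. The model uses two degrees of freedom (18 to 16 with 10 per arm). If the stratum adds nothing beyond the walk-1 value, the interval is about 1-2% wider than with the walk-1 value alone.

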Based on clinical practice and similarly to the dose used for breakthrough pain, we will use an FPNS dose equivalent to 15-25% of the MEDD (Table 3). For patients randomized to receive FPNS, the study medication will be provided by Dispensing Pharmacy and will then be administered intranasally 20 minutes before the second 6-minute walk test. The same dose will be repeated at least 30 minutes after the first dose and 20 minutes prior to the third and final 6 minute walk test. We estimated the FPNS dose based on the following assumptions:

- A rescue dose of 15-25% of the MEDD is safe and adequate for relief of dyspnea (Bruera *et al.* 1993, Charles *et al.* 2008).
- FPNS has approximately 80% oral bioavailability (Fisher *et al.* 2010, Fisher *et al.* 2010).
- With repeat dosing 30 minutes apart, the maximum concentration (C_{max}) for FPNS is approximately 1.6x higher than the first dose.

The modeled pharmacokinetic data for repeated dosing 30 minutes apart is shown in Figure 2. As a precautionary measure, patients will be asked to wait for 1 hour after completing the last walk before leaving MD Anderson. At the end of 1 hour, they will be assessed by our research staff before being released. If excessive drowsiness or adverse events occur, the study physician will assess the patients.

[figure not shown]

Figure 2. Modeled Pharmacokinetic Data on Repeat Dosing of Fentanyl Pectin Nasal Spray after 30 m

Table 3. Dose of Fentanyl Pectin Nasal Spray Based on Morphine Equivalent Daily Dose^a

| Morphine equivalent daily dose (mg) | Total Fentanyl Pectin Nasal Spray Dose (mcg) | Number of FPNS sprays | Number of Placebo sprays |
|-------------------------------------|--|-----------------------|--------------------------|
| | | | |

| | | | |
|---------|-----|--|---|
| 80-159 | 100 | 1 (100 mcg in one nostril) | 1 |
| 160-239 | 200 | 2 (100 mcg in each nostril) | 2 |
| 240-319 | 300 | 3 (100 mcg in one nostril and 2 x 100 mcg in the other nostril) ^b | 3 |
| 320-540 | 400 | 4 (2 x 100 mcg in each nostril) | 4 |

^aFPNS is available in 100 mcg.

^b For the 300 mcg dose, patients will receive 1 spray in each nostril, then another spray again in the one of the nostrils.

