C.10. Variable rest period. After the first and second 6 minute walk test, patients will be asked to sit down and rest. How long they rest would depend on when they return to baseline level of dyspnea numeric rating score + 1 or below (e.g. if baseline dyspnea = 4, they need to return to a level of 5 or less to qualify for next stage). During this rest period, patients will be assessed every 5 minutes to check their dyspnea level. If their dyspnea level met criteria and they feel ready to walk again, they will be given the study treatment and asked to wait for 20 minutes before they walk. At least 30 minutes should elapse between each dose of the study medication.

C.11. Stopping rules. Patients who do not develop any increase from their baseline dyspnea after the first 6-minute walk will not proceed to the next stage because of the lack of exercise induced dyspnea. If at any time during the study patients develop chest pain, severe leg cramps, staggering, diaphoresis, and/or dizziness, they will be asked to stop the study. If patients require more than 1 hour of rest and their dyspnea level still has not returned to baseline, they will also be taken off study. We plan to replace these patients and any other individuals who are not evaluable because they have not started the 2nd walk test.

C.12. Study assessments. See Table 4 for a detailed description of all study assessments.

Table 4. Summary of Study Assessments

| Assessments | Base-line | Post 1 st 6MWT | Rest #1 | Pre 2 nd 6MW | Post 2 nd 6MW | Rest #2 | Pre 3 rd 6MW | Post 3 rd 6MW |
|--|-----------|------------------------------|---------|----------------------------|-----------------------------|---------|----------------------------|-----------------------------|
| Demographics and cancer diagnosis ¹ | ✓ | | | | | | | |
| Medication history ² | ✓ | | | | | | | |
| Karnofsky performance status ³ | ✓ | | | | | | | |
| Edmonton Symptom Assessment Scale ⁴ | ✓ | | | | | | | |
| Dyspnea Survey ⁵ | ✓ | | | | | | | |
| Cancer Dyspnea Scale ⁶ | ✓ | | | | | | | |
| O ₂ saturation and respiratory rate | ✓ | ✓ | | ✓ | ✓ | | ✓ | ✓ |
| Dyspnea Numeric Rating Scale ⁷ | ✓ | ✓ | ✓ | ✓ | ✓ | ✓ | ✓ | ✓ |
| Dyspnea Borg scale ⁸ | ✓ | ✓ | ✓ | ✓ | ✓ | ✓ | ✓ | ✓ |
| Walking test parameters ⁹ | | ✓ | | | ✓ | | | ✓ |
| Adverse effects ¹⁰ | | | | ✓ | ✓ | | ✓ | ✓ |
| Neurocognitive testing ¹¹ | | ✓ | | | ✓ | | | ✓ |
| Global assessment ¹² | | | | | ✓ | | | ✓ |
| Blinding ¹³ | | | | | | | | ✓ |

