¹⁰ adverse effects related to the use of FPNS, such as dizziness, drowsiness, nausea, stuffy/blocked nose, runny nose, itching/sneezing, nose dryness, cough, sore throat, and taste disturbance will be assessed using a numeric rating scale from 0-10.

¹¹ patients will be asked to do finger tapping 10 and 30 sec, arithmetic, reverse memory of digits, and visual memory). This has been used in other studies by our group.(Bruera *et al.* 1992)

¹² patients will be asked about their dyspnea (worse, about the same, or better) comparing between the level of dyspnea between the first and second 6-minute walk tests (Guyatt *et al.* 1993, Redelmeier *et al.* 1996).

¹³ blinding will be done by asking patients which group assignment they received: "FPNS", "placebo", or "do not know".

¹⁴ study satisfaction is assessed with the following questions, "Was it worthwhile for you to participate in this research study?", "If you had to do it over, would you participate in this research study again?", "Would you recommend participating in this research study to others?", "Did you quality of life get better by participating in this research study?", "Did you quality of life get worse by participating in this research study?"

C.13. Feasibility data. In addition to clinical outcomes, we will also collect feasibility data in this study Rates of recruitment and retention (% of subjects able to complete the study)

- Reasons for refusal and dropout
- Outcome measure—we will compare the sensitivity of Numeric rating scale and Borg scale to change, and identify key measure for future study
- Participant satisfaction—participants will provide an opinion regarding their satisfaction with study overall

C.14. Patient Safety, Monitoring, and Confidentiality. During the study, trained research staff will be performing study assessments and monitoring the patients carefully throughout the study period. A study physician will also be available by pager to address any concerns, distress or questions, and will attend to the patient as needed. Patients will be doing the test in a hallway outside the Supportive Care Center which typically does not have a lot of traffic, and will have immediate access to medical and nursing care if needed. See stopping rules below for further details. With the planned

doses of fentanyl in opioid-tolerant patients, we do not expect any significant side effects.

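### Drowsiness, respiratory rate and SpO2 are recorded after dose 1, but no value of them withholds dose 2 and none is scheduled again during Rest #2.

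*Combined protocol and SAP*

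**What the plan says.** **Release of dose 2 (C.10).** The patient rests until the dyspnea NRS is at baseline + 1 or below. The check named for this period is of dyspnea only: "During this rest period, patients will be assessed every 5 minutes to check their dyspnea level". Then: "If their dyspnea level met criteria and they feel ready to walk again, they will be given the study treatment". Doses must be at least 30 minutes apart.

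**Stopping rules (C.11).** These apply at any time: if "patients develop chest pain, severe leg cramps, staggering, diaphoresis, and/or dizziness, they will be asked to stop the study". A patient who rests for more than 1 hour without dyspnea returning to baseline also comes off study.

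**Safety measures (C.9, Table 4).** Before and after each walk, staff record dyspnea "and the (2) respiratory rate and oxygen saturation". Footnote 10 adds 0-10 ratings of "adverse effects related to the use of FPNS, such as dizziness, drowsiness, nausea" and others. Both rows are ticked at Pre 2nd, Post 2nd, Pre 3rd and Post 3rd 6MW, and are blank at Rest #2.

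**Repeat dosing (C.7).** With doses 30 minutes apart, the Cmax "for FPNS is approximately 1.6x higher than the first dose". The schedule is judged safe on this ground: "Because this involves only 2 doses given to opioid tolerant patients, and under close monitoring by trained staff". Patients wait 1 hour after the last walk, and in that context: "If excessive drowsiness or adverse events occur, the study physician will assess the patients".

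**The concern.** The condition that releases dose 2 is the symptom the drug is given to reduce. A patient who is drowsy or breathing slowly after dose 1 may well report little dyspnea, and so meets C.10 more easily. The measures that would identify such a patient are already collected, but nothing in the plan links them to the dosing decision.

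What is at stake is patient safety at one step. Patients have exertional dyspnea, may be on oxygen at up to 6 L/min, and are about to receive a dose that the protocol itself expects to raise the peak concentration. As written, holding that dose depends on the judgement of whichever staff are present, and those staff do not know whether the patient received an opioid. Judgement may be good, but it will not be uniform, and the reason for a hold would not be recorded in a comparable way.

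**Working it through.** **Step 1. What is scheduled between the doses.** Inputs: dose 1 at 0 minutes, a 20-minute wait (C.7, C.10), a full 6-minute walk, and Table 4. *Pre* is taken to mean just before the walk, and *Post* immediately after it.

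| Table 4 column | Minutes after dose 1 | RR and SpO2 | Adverse effects, incl. drowsiness | Dosing action tied to these values |
|---|---|---|---|---|
| Pre 2nd 6MW | about 20 | yes | yes | none |
| Post 2nd 6MW | 20 + 6 = 26 | yes | yes | none |
| Rest #2 | 26 until dose 2 | no | no | none |
| Pre 3rd 6MW | dose 2 + 20 | yes | yes | none |

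Of Table 4's 15 rows, 2 are ticked at Rest #2: the dyspnea NRS and the Borg scale. B.3 gives a Tmax of 15-20 minutes, so the Pre 2nd reading falls at or just after dose 1's peak. Useful readings therefore exist before dose 2. What is missing is a rule that uses them, and a repeat at rest.

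**Step 2. Time from the last scheduled reading to dose 2.**
- Dose 2 at the 30-minute minimum: 30 − 26 = 4 minutes.
- Dose 2 at the first 5-minute rest check: 26 + 5 = 31, and 31 − 26 = 5 minutes.
- Full 1-hour rest: 26 + 60 = 86, and 86 − 26 = 60 minutes.

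If Pre 3rd falls after dose 2, the next reading comes 20 minutes after that dose, at or after its own Tmax. It cannot inform the decision to give the dose.

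**Step 3. How realistic the long interval is.** C.1 plans a visit of 1.5-2 hours. Three walks take 3 × 6 = 18 minutes and two waits take 2 × 20 = 40, together 58. That leaves 90 − 58 = 32 to 120 − 58 = 62 minutes for both rests, the surveys and neurocognitive testing. A 60-minute Rest #2 hardly fits.

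**Step 4. Where the 1.6-fold figure applies.** C.7 states it for doses 30 minutes apart. Dose 2 then comes 30 − 20 = 10 to 30 − 15 = 15 minutes after dose 1's peak, and the last reading is 4 to 5 minutes old. At 86 minutes the documents give no such figure. Accumulation and a stale reading are therefore separate reasons for a check, at opposite ends of the range.

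**Step 5. What a hold rule would cost.** D.1's figure first: for a two-sided paired t-test at 5% with effect size d, power = P(|T| > t(0.975, n−1)), where T is noncentral t with n−1 degrees of freedom and noncentrality d√n. With d = 1.0 and n = 10, power is 80.3%, which reproduces the stated 80%. With n = 9 it is 74.8%, and with n = 8 it is 68.1%. Applied to walk 1 versus walk 3, these show the cost of losing one or two patients' third walk. D.1 does not power that comparison, and the figures do not measure harm.

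The documents do not say how often a limit would be crossed. With an assumed rate p, the chance of at least one hold among 10 FPNS patients is 1 − (1 − p)^10: 40% for p = 5%, 65% for p = 10% and 89% for p = 20%.

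**The case against.** The strongest case against the point is that the plan is not silent on safety. All three measures are taken twice between dose 1 and dose 2, the first time near the expected peak, and neurocognitive testing follows walk 2. Dizziness and staggering, both plausible signs of opioid excess, end the study at any time and so prevent dose 2. The patient must feel ready to walk. Staff monitor throughout, a physician is on pager, patients take at least 80 mg of morphine equivalent daily, and there are only two doses of a drug approved for opioid-tolerant cancer patients.

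Most of this stands, and it rules out several stronger readings that a reader might infer:

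- *That nothing is checked between the doses.* Table 4 contradicts this at Pre 2nd and Post 2nd 6MW.
- *That C.10's conditions are the only barrier to dose 2.* C.11 is a second one.
- *That a 1.6-fold peak coincides with an hour without readings.* C.7 gives that figure for 30-minute spacing only.
- *That the regimen is unsafe.* Nothing in the documents shows this.

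The narrower point survives. Neither dizziness nor staggering need appear in a quietly sedated patient who is seated. The Post 2nd reading is taken straight after exercise, which can raise respiratory rate and alertness, so it is a weak guide to the patient's state at rest. C.7's sentence on drowsiness sits with the wait after the last walk and calls for assessment, not for withholding a dose. Close monitoring supplies observers but no criterion.

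**Conclusion.** The point holds as a cheap improvement for patient safety. No value of drowsiness, respiratory rate or SpO2 withholds dose 2 anywhere in the plan, and none of the three is scheduled during Rest #2. A sedated patient whose dyspnea has settled, and who has none of C.11's symptoms, meets the written conditions for a second dose.

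The last scheduled reading is about 4 to 5 minutes old at the shortest interval. It is older if Rest #2 is long, with about 60 minutes as an edge case. At the short end, the missing action limit matters more than the age of the reading.

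This rests on three assumptions: a full 6-minute walk, Post 2nd readings taken as soon as the walk ends, and Pre 3rd readings taken after dose 2. The last is the natural reading, since C.9 ties the check to the walk, but Table 4 does not state it. The frequency of over-sedation after dose 1 is unknown, so no size can be put on the harm avoided. The primary comparison is complete before dose 2 and is not in question.

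**What to change.** In C.10, C.11 and Table 4, for both arms:

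1. Record drowsiness NRS, respiratory rate and SpO2 at rest immediately before dose 2, and tick these at Rest #2.
2. Have the study physicians set a limit for each in advance. If any is crossed, withhold dose 2 and end the study after walk 2, keeping the 1-hour observation.
3. State whether the Pre 3rd readings come before or after dose 2.
4. Report holds by arm, separately from other reasons for no third walk, and describe walk 1 versus walk 3 results as applying to patients who received dose 2.

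The cost is a short amendment and a few minutes of the rest period; the measures and staff are already in the plan. Applying the rule in both arms keeps staff blinded.

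The real downside is selective loss. Third-walk data will be missing for the most sedated patients, and C.11 does not replace patients once walk 2 has started. Each hold in the FPNS arm removes about a tenth of that arm's third-walk data. D.1 counts patients as evaluable from the start of walk 2, so the primary endpoint loses nothing.
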